## **8.1 Subject Disposition**

Subjects will be summarized by the number and percent of subjects dosed, completed the study, and discontinued the study (with discontinuation reasons) by treatment (pooled placebo, active treatment, active treatment total) and overall.

## **8.2 Protocol Deviations**

Protocol deviations are captured by the clinical site and provided in the CSR in a similar format to that provided by the clinical site. Protocol deviations are not edited or processed in SAS®.

## **8.3 Demographics**

Descriptive statistics will be calculated for continuous variables (age, body mass index, height, and weight) by treatment (pooled placebo, active treatment, active treatment total) and overall. Age will be approximated by subtracting the year of birth from the year of informed consent. If year of informed consent – year of birth is one more than the protocol maximum age (65) then the age approximation will be year of informed consent – year of birth – 1. Descriptive statistics for body mass index, height, and weight will be calculated using screening measurements.

Frequency counts will be provided for categorical variables (sex, race, and ethnicity) by treatment (pooled placebo, active treatment, active treatment total) and overall.

## **8.4 Adverse Events**

All AEs occurring during this clinical trial will be coded using the Medical Dictionary for Regulatory Activities (MedDRA®), Version 26.1.

All AEs captured in the database will be listed in a by-subject data listing including dose group, verbatim term, coded term, treatment, onset date/time, resolution date/time, frequency, severity, relationship to study product, action, and whether the AE is an IR; however, only treatment-emergent AEs (TEAEs) will be summarized.

A TEAE is defined as an AE that is starting at the time of or after the start of study product administration. Each TEAE will be attributed to the treatment based on the onset date and time of the AE compared to that of the respective treatment administration start date and time.

If the onset time of an AE is missing and the onset date is the same as or occurs after the treatment dosing date, then the AE will be considered treatment emergent. If the onset date of an AE is missing, then the AE will be considered treatment emergent.

TEAEs will be tabulated by System Organ Class (SOC) and Preferred Term. Summary tables will include the number of subjects reporting the TEAE and as a percent of the number of subjects dosed by treatment (pooled placebo, active treatment, active treatment total) and

overall. The number of TEAEs will be tabulated in a similar manner. A table, which summarizes the number of TEAEs by Preferred Term, severity, and relationship to study product, will also be included.

SAEs if present, will also be listed. Applicable narratives will be included in the CSR.

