3.6 Study Pausing Criteria

Should any one of the following criteria occur, the Sponsor will stop study recruitment and will not administer IP to any subject until the SMC has reviewed all available study data:

- First occurrence of an AE with severity Grade 3 (Severe) or Grade 4 (Potentially Life-Threatening) considered to be at least likely related to TRL345
- 2 or more subjects with an AE of severity Grade 2 (Moderate) in the same body class considered to be at least likely related to TRL345 (among total number of subjects dosed)
- Any other toxicity which in the opinion of the SMC precludes further dosing.

Following review of safety data, the SMC will make a recommendation to continue the study as planned, to modify, or to terminate the study.

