8 STATISTICAL CONSIDERATIONS

8.1 Sample Size

No formal sample size calculations were performed. The numbers of subjects per dose level are typical for Phase 1 studies in healthy adult volunteers.

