8.5 Safety Analyses

8.5.1 Adverse Events

All AEs, including IRs, and SAEs, will be coded using the Medical Dictionary for Regulatory Affairs (MedDRA). Frequency tables will be presented by dose and treatment group for all AEs and SAEs by System Organ Class (SOC) and Preferred Term (PT). Frequency tables will also be produced by dose and treatment group for AEs leading to discontinuation from IP and study, by maximum severity, and by causality. No formal statistical testing will be done.

AEs and SAEs will be summarized overall, by severity, and relatedness, and may also be summarized within specific time intervals (e.g., within 4 hours of infusion).

Clinically significant physical exam and lab abnormalities will be reported as AEs and summarized as described above.

8.5.2 *Laboratory Evaluations and Vital Signs*

Quantitative data (e.g., clinical lab results) will be summarized by presenting mean, median, SD, and range by dose and treatment group. Laboratory abnormalities will be analyzed as safety outcomes by summarizing frequency, severity, and changes from baseline. Other analyses may include but are not limited to the following: examination of shift tables and pre-established severity grades. Additional serum samples will be taken and stored for possible exploratory analyses that may be necessary to further explore any unexpected safety or tolerability observations.

8.5.3 *Concomitant Medications*

Concomitant medications will be coded using the most current World Health Organization (WHO) drug dictionary and summarized by drug class and medication term, with results presented by dose and treatment group.

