### 3. STUDY DESIGN

This study is designed to meet the objectives outlined in [Section 2](#).

This is a Phase 1, first-in-human (FIH), double-blind, single ascending dose (SAD) study to assess the safety, PK, PD, and preliminary activity of TRL345. Healthy subjects aged 18-65, inclusive, will be screened.

Subjects who meet all inclusion and no exclusion criteria, will be enrolled into the study, assigned to a DG, and randomized to receive TRL345 or placebo. Each DG will include 8 subjects; 6 will receive TRL345 and 2 will receive placebo. An established ELISA assay available in commercial laboratories to detect Immunoglobulin (Ig) G antibodies against CMV will be used to determine serostatus of subjects prior to randomization. Dosing of the first two subjects (one randomized to TRL345 and one randomized to placebo) in each DG will be done on the same day. Dosing of the other subjects will occur at least 72 hours after the first two subjects have been dosed and following review of the blinded safety data from the first two subjects in the DG by the Principal Investigator (PI) and Sponsor. After all subjects within a DG have completed Day 15, a Safety Monitoring Committee (SMC) will review all available safety data through Day 15 prior to making a recommendation regarding escalation to the next higher DG.

Subjects will be admitted to a Phase 1 research unit prior to the IV administration of a single dose of TRL345 or placebo. In order to maintain the blind, subjects will be dosed as follows: DG1 will receive 1 mg/kg of TRL345 or 0.1 mL/kg of placebo and DG2 will receive 10 mg/kg of TRL345 or 1 mL/kg of placebo. All subjects (randomized to either TRL345 or placebo) will receive IP infused over 60 minutes.

Subjects will be closely monitored for AEs and SAEs, including infusion reactions (IRs), from the onset of the infusion through discharge from the Phase 1 research unit. Subjects will be assessed for safety and tolerability, including AEs and SAEs, at each follow-up visit after discharge through Day 76. A physical exam, vital signs, and routine clinical lab tests (chemistry and hematology) will be done on Days 1, 2, 3, 8, 15, 29, and 43. An electrocardiogram (ECG) will be done on Days 1 and 8.

Serum for PK will be collected on Days 1 (0, 1, 2, 4, 6, 12 hours after start of infusion), 2 (24 hours after start of infusion), and 3 (48 hours after start of infusion), and on Days 8, 15, 29, 43, and 76.

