## **8. SAFETY**

All relevant case report form (CRF) and clinical laboratory data will be listed by subject and chronologically by assessment time point. This will include rechecks, unscheduled, and early termination assessments.

Applicable continuous variables will be summarized using n, mean, SD, minimum, median, maximum, and range. Data from subjects who received the placebo treatment will be pooled across dose groups.

The level of precision will be presented as follows: minimum/maximum/range in the same precision as in the database, mean/median in one more precision level than minimum/maximum/range, SD in one more precision level than mean/median, and n will be presented as an integer. Percentages will be presented as an integer.

Where individual data points are missing because of dropouts or other reasons, the data will be summarized based on reduced denominators.

Baseline will be the result closest and prior to start of dosing unless otherwise stated. Summaries for post-baseline time points will not include rechecks, unscheduled, or early termination measurements.

Tables summarizing safety data by assessment time point will only include summaries for baseline and post-baseline time points.

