## **9. SUMMARY OF CHANGES FROM PROTOCOL-PLANNED ANALYSIS**

The protocol states that the following safety data will be summarized: physical examinations, medical history, disease history, concomitant medications, SAEs, AEs leading to discontinuation from study, AEs leading to discontinuation of study product, AEs within a specified time interval from dosing, and lab abnormalities (by severity). However, these analyses will not be performed and are not included in this SAP.

The protocol states that the all subjects receiving TRL345 will be included in the analyses. However, the Pharmacokinetic Population and the Pharmacokinetic Analysis Population were defined in this SAP for the PK analyses.

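### The protocol plans AE tables by maximum severity, but the SAP tabulates grade and relatedness only as event counts by Preferred Term, and SAP 9 does not declare the change

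*SAP*

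**What the plan says.** **Protocol.** Section 2.2.1 makes both the incidence and the severity of AEs part of the safety endpoint, and SAP 2 repeats this as the primary endpoint. Section 8.5.1 plans frequency tables by dose and treatment group for "AEs leading to discontinuation from IP and study, by maximum severity, and by causality". It then says that AEs and SAEs will be summarised overall, by severity and by relatedness.

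**SAP tables.** Besides the subject and event counts by System Organ Class (SOC) and Preferred Term, SAP 8.4 specifies one table with grade or relatedness: "A table, which summarizes the number of TEAEs by Preferred Term, severity, and relationship to study product, will also be included". In the list under 14.3.1 this is Table 14.3.1.3 (shell CAESR), whose title gives adverse events as the unit of count.

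**SAP listing.** The by-subject AE listing carries severity, relationship, "and whether the AE is an IR; however, only treatment-emergent AEs (TEAEs) will be summarized". The flag therefore reaches listing 16.2.7.1 and no table.

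**Declared changes.** SAP 9 names protocol analyses that will not be done, including summaries of SAEs, of AEs leading to discontinuation, and of "AEs within a specified time interval from dosing, and lab abnormalities (by severity"). A maximum-severity table is not on that list.

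**The concern.** Maximum severity is a property of the subject: each person is counted once, at the worst grade. An event count under a grade column is a different quantity and does not convert to the first when a subject has several events. In a first-in-human study whose primary endpoint includes AE severity, a reader of the report will want to know how many subjects in each dose group had nothing worse than Grade 1, how many reached Grade 2 or higher, and how many did so with an event judged likely related. As planned, none of these appears in a table, and the section meant to record departures from the protocol does not say so.

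**Working it through.** **Inputs.** The documents contain no design figure to reproduce: "No formal sample size calculations were performed" (Protocol 8.1). Group sizes come from SAP 3: "Each DG will include 8 subjects; 6 will receive TRL345 and 2 will receive placebo". With two dose groups, A = 6, B = 6 and Active Total = 12. SAP 8 says "Data from subjects who received the placebo treatment will be pooled across dose groups", so P = 2 + 2 = 4, and 6 + 6 + 4 = 16 overall. Full enrolment is assumed.

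**What each planned AE table holds.**

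| Table (shell) | Subjects counted | Events counted | Grade | Relatedness | SOC |
|---|---|---|---|---|---|
| 12-1 (IAES), 14.3.1.1 (CAES) | yes, by SOC and term | no | no | no | yes |
| 14.3.1.2 (CAEE) | no | yes, by SOC and term | no | no | yes |
| 14.3.1.3 (CAESR) | yes, per term, ungraded | yes, per term | event counts | event counts | no |

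CAESR shows grade and relatedness as two separate sets of columns and does not cross them. No table takes a subject's worst grade.

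**Can worst grade be recovered from these tables?** Take an active arm of 6. The event pattern below is constructed, and all events are judged likely related.

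*Several terms.* Subjects 1 and 2 each have one nausea event and one abdominal pain event.

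- Case X: subject 1 has both at Grade 2; subject 2 has both at Grade 1.
- Case Y: subject 1 has nausea at Grade 2 and pain at Grade 1; subject 2 has the reverse.

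In both cases:

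- CAES: 2 subjects with a TEAE, 2 under gastrointestinal disorders, 2 per term.
- CAEE: 4 events, 2 per term.
- CAESR: for each term 2 subjects, 2 events, 1 at Grade 1, 1 at Grade 2, 2 likely, 0 unlikely. Summing over the two terms gives 4 events, 2 at Grade 1 and 2 at Grade 2.

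The tables do not differ in any cell. The number of subjects who reached Grade 2 is 1 in case X and 2 in case Y.

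*Mixed grades within one term.* Suppose two subjects have three nausea events in all, two at Grade 2 and one at Grade 1. CAESR reads 2 subjects, 3 events, 1 and 2. Subject 1 may have both Grade 2 events and subject 2 the Grade 1 event (1/6 at Grade 2), or each may have one Grade 2 event and one of them also the Grade 1 event (2/6). Again the row is the same.

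**Size of the ambiguity.** Exact (Clopper-Pearson) 95% limits for x of n are the 2.5% point of Beta(x, n − x + 1) and the 97.5% point of Beta(x + 1, n − x).

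- x = 1, n = 6: 1/6 = 16.7%, limits 0.4% to 64.1%.
- x = 2, n = 6: 2/6 = 33.3%, limits 4.3% to 77.7%.

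The same tables fit a Grade 2 incidence of 17% or 33% in that arm.

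**The case against.** **The data are not lost.** A reader might infer that the incidence of graded AEs goes unreported. The documents do not support that. Listing 16.2.7.1 shows every AE by subject with SOC, term, grade, relationship and infusion-reaction flag, and with 16 single-dose subjects a hand count is feasible. The figures are not tabulated; they are not missing from the report.

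**CAESR has a subject column.** A reader might infer that repeated events in one subject always look like events in several subjects. When all events under a term share one grade, the subject column of CAESR separates the two situations and is itself the incidence at that grade. The ambiguity needs mixed grades or more than one term, as in the examples above.

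**The pausing criteria.** Protocol 3.6 counts "2 or more subjects with an AE of severity Grade 2 (Moderate) in the same body class", so it is tempting to say that the final tables must be able to verify this rule. No document gives them that task. The rule operates during the study, through the Safety Monitoring Committee's review of all available study data.

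**Infusion reactions.** Protocol 8.5.1 includes infusion reactions among the AEs to be coded but asks for no separate table. The dropped time-from-dosing summary was optional in the protocol, and SAP 9 declares its removal. Neither document says whether a reaction is entered as one AE or several, and neither ranks infusion reactions first among the expected risks. The absence of an infusion-reaction count is therefore not a breach of the protocol.

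**The protocol sentence can be read narrowly.** The words on maximum severity share a sentence with AEs leading to discontinuation, a summary that SAP 9 does drop, and CAESR answers the general request for AEs by severity and relatedness at event level. By causality does not necessarily mean by subject, and the protocol does not ask for grade crossed with relatedness or severity within SOC. These are fair points. But the sentence reads more naturally as three sets of tables, and SAP 9 drops the first without mentioning the second. Even on the narrow reading, the primary endpoint still has no subject-level table by grade.

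**Shells may change.** SAP 11 says so, but the text of SAP 8.4 and the title of Table 14.3.1.3 also specify event counts.

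**Conclusion.** The point holds as a gap in tabulation and in the record of changes. Protocol 8.5.1 plans tables by maximum severity; no SAP table provides one; SAP 9 does not declare its absence. The gap bears on the primary safety endpoint, but its size is limited: this is a descriptive study with no formal testing, ungraded subject incidence is tabulated per term and per SOC, and the by-subject listing allows a hand count. In the constructed example the tables cannot distinguish 1/6 from 2/6 subjects at Grade 2. That rests on full enrolment of 6 per active arm, on the grade columns of CAESR being event counts as its title says, and on an event pattern with mixed grades. If no subject has more than one TEAE, worst grade can be recovered by adding CAESR's grade columns over terms. Trial conduct is not affected, and the infusion-reaction count is a desirable addition only.

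**What to change.** Add to SAP 8.4 and Section 14.3.1 one table giving the number and percent of subjects dosed by maximum severity (Grades 1 to 4), overall and by SOC, for all TEAEs and again for likely-related TEAEs, with columns P, A, B and Active Total. The denominators at full enrolment are 4, 6, 6 and 12. Keep CAESR as a supporting event table. If the sponsor prefers not to add the table, SAP 9 should list it as a protocol-planned analysis that will not be done.

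Optionally, add a row with the number and percent of subjects with at least one AE flagged as an infusion reaction. The protocol does not require it, but the flag is already collected.

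The cost is a few lines of SAP text, one shell and a small amount of programming from variables already in the AE listing. No new data are needed. It is better specified now, because SAP 1 treats additional exploratory or sponsor-requested analyses as out of scope.

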## 8.5 Clinical Laboratory Tests (Chemistry and Hematology)

Clinical laboratory tests will be measured at the following time points:

Clinical Laboratory Panels	Time Point		
	Period	CRF/Listing Day and Hour	Table
Chemistry, Hematology	Screening		NA
	1	Day -1 Hour -23.00/-22.75*^	Baseline
		Day 2 Hour 24.00	Day 2
		Day 3 Hour 48.00^	Day 3
		Day 8 Hour 168.00	Day 8
		Day 15 Hour 336.00*^	Day 15
		Day 29 Hour 672.00*^	Day 29
		Day 43 Hour 1008.00^	Day 43

Time points in the CRF/Listing column are approximated/based on the blank CRF and it should be noted that the data listings will reflect the data found in the final subject CRFs.

If applicable, an early termination assessment will be performed.

\*hsCRP and LDH will be collected at these time points and included in the Chemistry TFLs.

^NT-proBNP and IL-1 $\alpha$  will be collected at these time points and included in the Chemistry TFLs.

NA = Not applicable (individual result(s) may be required for baseline)

Clinical laboratory results will be presented in standard international (SI) units. Out-of-reference range flags will be recorded as follows: high (H) and low (L) for numerical results and did-not-match (\*) for categorical results.

Out-of-reference range values and corresponding recheck results will be listed.

For all numeric laboratory values, descriptive statistics will be presented for each laboratory test by assessment time point and treatment (pooled placebo and active treatment). Change from baseline will be summarized in a similar manner. For all numeric laboratory tests, the mean value calculated for each assessment time point and treatment will be compared to the reference range and flagged if outside of the reference range (\* if above the reference range and ^ if below the reference range). In the event there is more than one reference range for a laboratory test, the comparison will be made against the lowest of the lower ranges and the highest of the higher ranges.

For each laboratory test, a shift table will be developed to compare the frequency of the results at baseline (above reference range, within reference range, or below reference range) with the respective postdose results.

## 8.6 Vital Signs

Vital signs will be measured at the following time points:

Parameter	Time Point		
	Period	CRF/Listing Day and Hour	Table
Blood Pressure, Pulse, Temperature	Screening		NA
	1	Day 1 Hour -0.75	Baseline
		Day 1 Hour 0.25	Day 1, Hour 0.25
		Day 1 Hour 0.50	Day 1, Hour 0.50
		Day 1 Hour 0.85	Day 1, Hour 1
		Day 1 Hour 1.85	Day 1, Hour 2
		Day 1 Hour 5.00	Day 1, Hour 5
		Day 2 Hour 23.85	Day 2
		Day 3 Hour 47.85	Day 3
		Day 8 Hour 167.92	Day 8
		Day 15 Hour 335.85	Day 15
		Day 29 Hour 671.85	Day 29
		Day 43 Hour 1007.85	Day 43

Time points in the CRF/Listing column are approximated/based on the blank CRF and it should be noted that the data listing will reflect the data found in the final subject CRFs.

If applicable, an early termination assessment will be performed.

NA = Not applicable (individual result(s) may be required for baseline)

Descriptive statistics will be presented for vital signs measurements by assessment time point and treatment (pooled placebo and active treatment). Change from baseline will be summarized in a similar manner.

## 8.7 Electrocardiogram

ECGs will be measured at the following time points:

Parameter	Time Point		
	Period	CRF/Listing Day and Hour	Table
HR, RR, PR, QRS, QT, QTcF	Screening		Baseline
	1	Day 1 Hour 4.75, 4.77, 4.78	Day 1
		Day 8 Hour 167.75, 167.77, 167.78	Day 8

Time points in the CRF/Listing column are approximated/based on the blank CRF and it should be noted that the data listing will reflect the data found in the final subject CRFs.

ECGs will be collected in triplicate. The triplicate measures will be averaged and rounded to the nearest tenth. The averages will be used in all summaries.

Only valid ECGs will be used to calculate average ECG values for each parameter that will be used in the analysis. Valid ECGs do not include records of questionable quality. These include, but are not limited to, records with an associated comment indicating an artifact, lead reversal, wandering lead, etc. ECGs collected in error will also not be classified as valid ECGs. After excluding these ECGs, the remaining ECGs for the respective triplicate set will

be assessed against a time window of 10 minutes. A triplicate ECG set is expected to be performed within a 5-minute window but a 10-minute window is selected to increase the likelihood of having a full triplicate ECG set for the calculation of the average ECG value. The start of the window for a given postdose time point will be equivalent to the time of the first valid ECG. ECGs that fall outside of the 10-minute window will not be considered valid ECGs. At a given time point, if it is not possible to form a complete ECG triplicate set of valid results, the average will be calculated using the available valid results, i.e., the average of 2 valid ECGs or the single valid ECG result will be used in the analysis. Averaged ECG values will be displayed to the nearest tenth and used in the analysis.

Descriptive statistics will be presented for the by-subject averages of each ECG parameter by assessment time point and treatment (pooled placebo and active treatment). Change from baseline will be summarized in a similar manner. Baseline is defined as the average of the valid ECG set closest and prior to start of dosing which may include unscheduled assessments. This will typically be the average of the triplicate ECG set collected at Screening. At postdose time points, the average of the first valid ECG set will be used in the analysis. Postdose unscheduled and early termination measurements will not be included in summaries.

All ECG data will be listed by-subject and QTc values > 450 msec will be flagged. A separate by-subject listing will be provided to display the ECG average values to be used during analysis where QTc average values > 450 msec and increase from baseline > 30 msec will be flagged.

